3.3.2 Supportive secondary endpoint(s)

Not applicable

3.4 TERTIARY/EXPLORATORY ENDPOINT(S) ANALYSIS

3.4.1 Definition of endpoint(s)

[REDACTED]

3.4.2 Main analytical approach

[REDACTED]

3.5 MULTIPLICITY ISSUES

No formal testing will be performed. Therefore, no multiplicity issues need to be addressed.

3.6 SAFETY ANALYSES

All safety analyses will be performed on the exposed population as defined in [Section 2](#).

The analysis of the safety variables will be descriptive, and no testing is planned.

3.6.1 Extent of exposure

If applicable, summaries will be provided by trial impact (disruption) due to COVID-19.

3.6.1.1 *Overall exposure*

The dose information will be assessed by the following variables:

- Overall number of cycles started, defined by the number of cycles in which at least one dose of any study interventions is administered.
- Duration of IMP exposure (in months) is defined as (Last day of exposure – first day of exposure +1)/30.4375.
- The first day of exposure is defined as the first administration date with non-zero dose for at least one of the IMP (SAR444245 or pembrolizumab).

The last day of exposure is the day before the theoretical date of the next administration (after the last administration), defined as the maximum between:

For cohort A

- The last administration date + 20 days for SAR444245
- The last administration date + 20 days for pembrolizumab

For cohort C1

- The last administration date + 13 days for SAR444245

The total number of cycles started, and number of cycles started by participants will be summarized by category.

The duration of overall exposure will be summarized quantitatively.

The following variable will be computed to describe overall dose modification (cycle delay):

- Cycle delay: A cycle is deemed as delayed if the start date of the current cycle – theoretical duration of a cycle – start date of the previous cycle is \geq 4 days (in cohort A); \geq 3 days in cohort C1. Cycle delay is not defined for the first cycle.

Cycle delay will be analyzed at the participant (with number of participants used as denominator) and cycle (with number of cycles used as denominator) levels, as follows:

- Number (%) of participants with at least 1 cycle delayed
 - Number (%) of participants with a cycle delayed between 4 and 7 days (using maximum delay across all cycles)
 - Number (%) of participants with a cycle delayed $>$ more than 7 days (using maximum delay across all cycles)
- Number (%) of cycles delayed
 - Number (%) of cycles delayed between 4 and 7 days
 - Number (%) of cycles delayed $>$ more than 7 days

3.6.1.2 SAR444245 exposure

The dose information will be assessed by the following:

- Total number of cycles started per participants
- Duration of SAR444245 exposure (in months) is defined by (date of last administration of SAR444245 + X – date of first administration of SAR444245) / 30.4375 (X equals 20 for cohort A, and 13 for cohort C1)
- Actual dose (μ g/kg)
- Cumulative dose (μ g/kg): the cumulative dose is the sum of all actual doses of SAR444245, given from first to last administration

- Actual dose intensity (ADI in $\mu\text{g}/\text{kg}/\text{week}$): defined as the cumulative dose divided by the duration of SAR444245 exposure (in weeks)
- Planned dose intensity (PDI in $\mu\text{g}/\text{kg}/\text{week}$): corresponds to the planned C1D1 dose divided by the theoretical cycle duration expressed in weeks (i.e., 3 weeks)
- Relative dose intensity (RDI, in %): $100 \times \frac{\text{ADI} (\mu\text{g}/\text{kg}/\text{week})}{\text{PDI} (\mu\text{g}/\text{kg}/\text{week})}$

The total number of doses, total number of cycles started, number of cycles started by participant will be summarized by category. Duration of SAR444245 exposure, cumulative dose, ADI and RDI will be summarized quantitatively. RDI will also be summarized by category if relevant.

The following variables will be derived to describe dose modifications and dose interruptions:

- Dose reduction: The first administration will not be counted as a dose reduction. For the second and subsequent SAR444245 administrations, dose reduction will be determined using the dose level intervals provided in [Table 6](#), by comparing the current dose level to the previous dose level. If the current dose level is below the dose level interval of the previous dose administration, then the current dose level is considered reduced.

Table 6 – SAR444245 dose reduction criteria

Actual dose level	Dose level interval
8 $\mu\text{g}/\text{kg}$	
16 $\mu\text{g}/\text{kg}$	
24 $\mu\text{g}/\text{kg}$	

- Dose omission is defined as a dose not administered at the scheduled visit.
- Dose interruption: a dose will be considered as interrupted if SAR444245 administration is stopped during an infusion regardless of whether it is restarted or not.

Dose modifications and dose interruptions will be analyzed by participant and dose as follows:

- Participant** (number of participants treated will be used as denominator)
 - Number (%) of participants with at least 1 dose modification
 - Number (%) of participants with at least 1 dose reduction
 - Number (%) of participants with at least 1 dose omission
 - Number (%) of participants with at least 1 dose interrupted
 - Number (%) of participants with at least 1 dose interrupted and restarted
 - Number (%) of participants with at least 1 dose interrupted and not restarted
 - Number (%) of participants with at least 2 dose interruptions
- Dose** (number of doses started will be used as denominator)

- Number (%) of doses
- Number (%) of doses interruptions
- Number (%) of doses interruptions and restarted
- Number (%) of doses interruptions definitively stopped
- Number (%) of doses interruptions more than once
- Number (%) of doses interrupted at 1st dose, 2nd dose, subsequent doses
- Time from dose start to first interruption in minutes summarized as a continuous variable and by category.

3.6.1.3 *Pembrolizumab exposure (cohort A)*

The dose information will be assessed by the following:

- Total number of cycles started per participant
- Duration of pembrolizumab exposure (in weeks) is defined by (date of last administration of pembrolizumab + 21 – date of first administration of pembrolizumab) /7
- Actual dose (mg)
- Cumulative dose (mg): the cumulative dose is the sum of all actual doses of pembrolizumab, given from first to last administration
- Actual dose intensity (ADI in mg/week): defined as the cumulative dose divided by the duration of pembrolizumab exposure (in weeks)
- Planned dose intensity (PDI in mg /week): corresponds to the planned dose at C1D1 divided by the theoretical cycle duration expressed in weeks (i.e., 3 weeks per cycle started)
- Relative dose intensity (RDI, in %): $100 \times \frac{\text{ADI (mg/week)}}{\text{PDI (mg/week)}}$

The total number of doses, total number of cycles started, number of cycles started by participant will be summarized by category. Duration of pembrolizumab exposure, cumulative dose, ADI and RDI will be summarized quantitatively. RDI will also be summarized by category if relevant.

The following variables will be derived to describe dose modifications and dose interruptions:

- Dose omission is defined as a dose not administered at the scheduled visit.
- Dose interruption: a dose will be considered to be interrupted if the pembrolizumab administration is stopped during an infusion regardless of whether it is restarted or not.

Dose modifications and dose interruptions will be analyzed by participant as follows:

- **Participant** (number of participants treated will be used as denominator)
 - Number (%) of participants with at least 1 dose omission

- Number (%) of participants with at least 1 dose interruption
 - Number (%) of participants with at least 1 dose interruption restarted
 - Number (%) of participants with at least 1 dose interrupted and not restarted
- Number (%) of participants with at least 2 dose interruptions

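### SAR444245 exposure is counted one day short in the SAP, so RDI exceeds 100% under perfect dosing; in Cohort C1 the 3-week PDI divisor and the delay sub-rows also do not fit the 2-week schedule

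*SAP*

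**What the plan says.** SAP 3.6.1 contains three duration rules and one delay rule.

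- **Overall exposure (3.6.1.1).** The duration in months is "Last day of exposure – first day of exposure +1)/30.4375". For Cohort A the last day is the later of two dates, one per drug, the first being "The last administration date + 20 days for SAR444245"; the pembrolizumab offset is the same. For Cohort C1 it is "The last administration date + 13 days for SAR444245".
- **SAR444245 exposure (3.6.1.2).** The duration is the last administration date plus X minus the first, where "X equals 20 for cohort A, and 13 for cohort C1". There is no +1. ADI is "defined as the cumulative dose divided by the duration of SAR444245 exposure (in weeks"). PDI is the planned C1D1 dose over the planned cycle length, for which 3 weeks is the only value given. RDI is ADI as a percentage of PDI.
- **Pembrolizumab exposure (3.6.1.3, Cohort A only).** The duration runs to "date of last administration of pembrolizumab + 21", less the first administration date.
- **Cycle delay (3.6.1.1).** The threshold is at least 4 days in Cohort A and at least "3 days in cohort C1. Cycle delay is not defined for the first cycle". The sub-rows under the total are "Number (%) of participants with a cycle delayed between 4 and 7 days" and more than 7 days, with the same split at cycle level and no separate version for C1.

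The cycle is 21 days in Cohort A and 14 days in C1 (footnote b to the Schedule of Activities, section 1.3 of substudies 01 and 03). The delay thresholds match section 6.5.2 of each substudy.

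**The concern.** The offsets 20 and 13 locate the last day covered by a dose, which is the day before the next one is due. They become a length of time only when both end days are counted. The overall formula does this with its +1, and the pembrolizumab formula does it by using 21. The SAR444245 formula keeps the end-date offsets and omits the +1.

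ADI divides by this duration, so the slip passes into RDI and always overstates delivered intensity. It is proportionally largest in participants with few doses. Such participants are foreseeable, because both substudies' infusion-reaction tables require permanent discontinuation of SAR444245 after a Grade 3 or 4 reaction clearly attributable to it.

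For Cohort C1, two further items appear not to have been adapted when dosing moved to every 2 weeks: the PDI divisor and the delay sub-rows. Tables programmed from this text would disagree with one another in C1, and the C1 RDI would not be interpretable.

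**Working it through.** The SAP gives no numerical RDI to reproduce, so its formulas are applied to a participant who receives n full doses exactly on schedule.

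**Inputs.** L = 21 days (A) or 14 days (C1). X = 20 or 13. Pembrolizumab offset 21. Maximum cycles 35 (A) and 52 (C1), from section 4.1 of each substudy. Weeks are taken as days/7. The dose per administration cancels.

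**Durations in days.** First to last dose is L(n − 1).

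- SAR444245: L(n − 1) + X = Ln − 1
- Overall: L(n − 1) + X + 1 = Ln
- Pembrolizumab: 21(n − 1) + 21 = 21n

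In Cohort A, SAR444245 / overall / pembrolizumab are 20/21/21 at one cycle, 125/126/126 at six and 734/735/735 at 35. In C1, SAR444245 / overall are 13/14 at one cycle, 83/84 at six and 727/728 at 52. The gap is always one day, or 1/30.4375 = 0.033 months.

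**RDI under perfect dosing.**

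- Cohort A, 3-week divisor: 100 × 21n/(21n − 1)
- C1, 2-week divisor (one-day effect alone): 100 × 14n/(14n − 1)
- C1, 3-week divisor as printed: 100 × 21n/(14n − 1)

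| Cycles | Cohort A | C1, 2-week divisor | C1, 3-week divisor |
|---|---|---|---|
| 1 | 105.00% | 107.69% | 161.54% |
| 2 | 102.44% | 103.70% | 155.56% |
| 4 | 101.20% | 101.82% | 152.73% |
| 6 | 100.80% | 101.20% | 151.81% |
| Maximum (35 / 52) | 100.14% | 100.14% | 150.21% |

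**After correction.** With X = L the SAR444245 duration is Ln. Cohort A RDI is then 100.00% at every n. C1 RDI is 100.00% only if the divisor is also 2 weeks. Correcting X alone leaves 100 × 21n/14n = 150.00%; correcting the divisor alone leaves the third column.

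**Delay rows, whole days.** In Cohort A every delay of 4 days or more falls in 4–7 or >7. In C1 a delay of exactly 3 days meets the definition and falls in neither. At participant level the sub-rows use the longest delay, so a C1 participant whose longest delay is 3 days appears only in the total.

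**The case against.** **The effect is small and fades.** This stands. It is one day, worth 0.8 RDI points at six Cohort A cycles and about 0.14 at the maximum in either cohort. Permitted dosing windows move RDI more. With the corrected duration, two Cohort A doses given 3 days early or late yield 42/39 = 107.7% or 42/45 = 93.3%. The ±2-day C1 window with a 2-week divisor yields 28/26 and 28/30, the same percentages. A reader might therefore infer that any RDI above 100% reveals the error, but the windows alone can produce such values. What distinguishes the slip is that it affects every participant in the same direction.

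**Cohort A tables may differ by design.** This also stands. Overall exposure there takes the later of two drugs, either of which may continue alone, and only SAR444245 may be dose-reduced. A reader might infer that any mismatch in Cohort A is an error; the clear contradiction between tables is in C1. The pembrolizumab comparison is sound for duration on shared dosing dates. It is less clean for RDI, because 3.6.1.3 words its PDI divisor in terms of cycles started, which could be read as growing with the number of cycles.

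**The 3-week figure may be only an illustration.** If the reference to planned cycle length governs, the 2-week C1 column applies. The text does not say so and gives no C1 value, so both readings are shown.

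**The missing delay row loses no information.** This is correct: 3-day delays equal the total minus the two sub-rows. It is a layout gap.

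**Conclusion.** The SAP is wrong as written, but the consequence is limited. The SAR444245 duration is one day short in both cohorts. Under perfect dosing this adds 5.0 RDI points (A) or 7.7 points (C1, 2-week divisor) after one cycle, and about 0.14 at the maximum number of cycles. It matters mainly for participants who stop after one or two cycles.

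The larger C1 distortion, about 150% to 162%, arises if the printed 3-week divisor is applied. A reader might attribute all of it to the missing day, or expect that changing X alone restores 100% in C1; neither is supported, since the divisor by itself produces 150%.

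Nor do the documents support an inference that the efficacy results are at risk. These are descriptive summaries, and CRR, ORR, DoR and PFS do not use them. Cumulative dose, cycles started, and counts of reductions, omissions and interruptions are also untouched.

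The figures assume full doses exactly on schedule and weeks computed as days/7.

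**What to change.** Make three edits to SAP 3.6.1:

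1. In 3.6.1.2 set X to 21 for Cohort A and 14 for Cohort C1, or keep 20 and 13 and add 1 to the formula.
2. In 3.6.1.2 set the SAR444245 PDI divisor to the cohort's cycle length: 3 weeks for Cohort A and 2 weeks for C1.
3. In 3.6.1.1 define the C1 delay sub-rows as 3–7 days and more than 7 days, at participant and cycle level, and leave Cohort A as it is.

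Edits 1 and 2 are both needed for C1. The cost is a few lines of SAP wording and the matching programming. No new data are needed, and no dosing rule or efficacy analysis changes.

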Intervention groups and duration:

Please refer to the master protocol for common descriptions of the study duration. For Cohort C1, the maximum cycles allowed are 52 cycles.

Study interventions**Cohort C1: DLBCL participants with stable disease or progressive disease 1-3 months after receiving a Health Authority approved CAR-T as at least 3L therapy**

Dosing sequence: premedication for SAR444245 (30 to 60 minutes prior to start of SAR444245 infusion), and SAR444245.

Investigational medicinal products

SAR444245

SAR444245 formulation and route of administration as described in the master protocol.

- Dose regimen: 24 µg/kg administered (or reduced to █ µg/kg or another lower dose level recommended by Study Board) as an IV infusion over 30 minutes every 2 weeks on Day 1 of each cycle (14 days per cycle) for **up to 52 cycles**.

Non-investigational medicinal products

Please refer to the master protocol.

Statistical considerations:

Please refer to the master protocol for descriptions of common statistical considerations. Substudy-specific analyses are summarized below.

[figure not shown]
- **Analysis of primary endpoint:**
 - The objective response rate (ORR) will be summarized for the efficacy population with descriptive statistics. In addition, two-sided 90% CIs for ORR will be computed using the Clopper-Pearson method.
- **Analysis of secondary efficacy endpoints:**
 - The complete response rate (CRR) will be summarized for the efficacy population with descriptive statistics. In addition, two-sided 90% CIs for CRR will be computed using the Clopper-Pearson method.

Data Monitoring/Other Committee: Yes

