a Evaluation: Screening assessments to be performed prior to first IMP administration unless otherwise indicated. Baseline evaluations should be completed within 7 days prior to the first dose of IMP, except for tumor assessment that may be performed within 28 days prior to IMP administration, and unless specified otherwise. There is no need to perform Cycle 1 Day 1 laboratory assessments that have been performed as part of screening within 3 days prior to first IMP administration. During the study treatment period, all assessments must be performed, and results should be reviewed by the investigator **prior to IMP administration** at that visit. After Cycle 1, samples for laboratory assessments (excluding PK & biomarker) can be collected up to 2 days prior to IMP administration. ICF must be signed before any study-specific procedures are performed and can be signed more than 28 days prior to first IMP administration. Screening time indicates the maximum time frame relative to the first IMP administration in which study procedures used to support eligibility are done.

- b Cycle: A treatment cycle is 14 days. See details in [Section 6.1](#) for IMP administration. If treatment cycles are adjusted, all procedures except tumor assessment imaging will be completed according to the Cycle number. Tumor assessment imaging will be performed at fixed time points from C1D1 regardless of any treatment delays.
- c Observation Period: Participants who enter the Observation period will be followed differently depending on the reason leading to permanent study treatment discontinuation. See Section 4.1 of the master protocol. For participant's convenience, all Follow-up assessments may occur during the same visit as that when tumor assessment is performed.
- d Survival Phone Call Follow-Up Period: Once the participant stops the tumor assessments due to PD or starts a new antineoplastic therapy, the participant moves into the Survival Follow-up Period and should be contacted by telephone approximately every 3 months \pm 14 days to assess for survival status. Updated survival status may be requested by the Sponsor at any time during the study.
- e Visits on C1D2, D3 are for safety-run in participants only.

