3 STATISTICAL ANALYSES

3.1 GENERAL CONSIDERATIONS

In general, continuous data will be summarized using the number of observations available, mean, standard deviation (SD), median, minimum, and maximum. Categorical and ordinal data will be summarized using the count and percentage of participants.

The baseline value is defined as the last available value before the first administration of any of the two IMPs (SAR444245 or pembrolizumab). For participants enrolled but not treated, the baseline value is defined as the last available value before enrollment.

Unless otherwise specified, analyses will be performed by cohort, by dose level (if applicable) and overall. Participants enrolled in the safety run-in part and treated at the RP2D will be included in the analyses of the core part.

All efficacy analyses will be performed on the efficacy population. Complete response rate (CRR, for cohort A) and objective response rate (ORR, for cohort C1), as well as all other response-related efficacy endpoints will be derived using the Investigator's assessment per Lugano response criteria 2014 for all cohorts.

All safety analyses will be performed on the exposed population.

Central imaging may be done retrospectively if significant activity is observed (See [Section 3.2.3](#) for sensitivity analysis).

Confidence intervals will be two-sided 90% CI for efficacy analyses. CI will be used for descriptive purposes only, without inference.

The BOR is defined as the best overall response observed from the date of first IMP until disease progression, death, cut-off date or initiation of subsequent anti-cancer therapy, whichever occurs first.

Analysis period

The analysis period will be divided into 3 segments:

- The **pre-treatment period** is defined as the time from when the participants give informed consent to the first administration of the IMP.
- The **on-treatment period** (i.e., treatment-emergent (TE) period) is defined as the time from the first administration of IMP up to 30 days after the last administration of IMP.
- The **post-treatment period** is defined as the time from the end of the on-treatment, ie. 31 days after the last administration of IMP.

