1	28-Apr-2022	Sub-study 03; 6.5.2 Cycle delay: The section has been updated to clarify the treatment windows within a cycle, and the dose delay and omission rules. The title of the section was renamed as "Dose delay and dose omission" accordingly.	To align with the Cohort C1 Q2W dosing.
1	28-Apr-2022	Sub-study 03; 8.1 Efficacy assessment: Table 7 for imaging or disease assessment collection plan has been newly added, and details on efficacy assessments based on CAR-T trial experience have been added.	For clarity
1	28-Apr-2022	Sub-study 03; Throughout: The duration for each cycle has been changed from "21 days" to "14 days". The total number of cycles has been changed from "35 cycles" to "52 cycles".	To align with the Cohort C1 Q2W dosing.

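### The SAP sets one 3-week divisor for SAR444245 planned dose intensity, but Cohort C1 has a 14-day cycle, so its relative dose intensity is overstated by a factor of 1.5

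*SAP*

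**What the plan says.** SAP 3.6.1.2 covers SAR444245 exposure in both cohorts. Actual dose intensity (ADI) is cumulative dose over exposure duration in weeks. PDI "corresponds to the planned C1D1 dose divided by the theoretical cycle duration expressed in weeks (i.e., 3 weeks"). RDI is 100 × ADI/PDI, and "RDI will also be summarized by category if relevant".

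The divisor has no cohort split. The exposure duration in the same list does: "X equals 20 for cohort A, and 13 for cohort C1". SAP 3.6.1.1 also splits the last day of exposure (last SAR444245 dose plus 20 days in A, plus 13 in C1) and the delay threshold (4 days in A, 3 in C1).

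Substudy 03 is unambiguous about C1. Its Synopsis gives dosing "every 2 weeks on Day 1 of each cycle (14 days per cycle"), and footnote b of its Schedule of Activities says "A treatment cycle is 14 days". Cohort A (Substudy 01) has a 21-day cycle.

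SAP 3.1 states that, unless otherwise specified, "analyses will be performed by cohort, by dose level (if applicable) and overall".

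**The concern.** The words that govern the definition refer to the theoretical cycle length, which is 2 weeks in C1. The parenthesis then gives a single value, 3 weeks, introduced as an equivalent and not as an example. For C1 the definition and its stated value disagree, and nothing elsewhere resolves it. SAP 3.9 records for Substudy 03 that "The duration for each cycle has been changed from" 21 to 14 days, so the 3 weeks may be a remnant of the longer cycle; the documents do not establish that.

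RDI is the one exposure statistic expressed as a percentage of planned intensity. A reader would use it to judge whether a weak C1 response, or a mild toxicity profile, goes with incomplete delivery. The error runs in the unhelpful direction: delivery well short of plan would print as full or better. Substudy 03, section 6.5.2, allows a restart after delays of up to 84 days, so reduced intensity is a realistic outcome. If RDI is tabulated by category, C1 participants could land in the wrong one. If an overall row is produced, it would combine a correct Cohort A divisor with a wrong C1 divisor.

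**Working it through.** **Inputs.** Planned dose 24 µg/kg (Substudy 03 Synopsis; it cancels in the ratio). Cycle length 21 days in A and 14 in C1 (substudy synopses). Duration offset X = 20 in A and 13 in C1 (SAP 3.6.1.2). PDI divisor 3 weeks (SAP 3.6.1.2).

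**The stated divisor.** Cohort A: 21/7 = 3 weeks, reproduced. Cohort C1: 14/7 = 2 weeks, not reproduced.

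**PDI.** Cohort A: 24/3 = 8 µg/kg/week. Cohort C1 as written: 24/3 = 8. Cohort C1 on its own cycle: 24/2 = 12.

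**Ratio.** ADI does not involve the divisor, so RDI as written over RDI corrected = 12/8 = 1.5, whatever the dose, number of doses or delays.

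**RDI for C1 at full dose.** With n doses at a mean interval of I days and X = 13, ADI = 24n / ((I(n−1) + 13)/7). RDI as written is 100 × ADI/8; with the 2-week divisor it is 100 × ADI/12.

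| Interval I (days) | Doses n | ADI (µg/kg/week) | RDI as written | RDI, 2-week divisor |
|---|---|---|---|---|
| 14 | 1 | 12.92 | 161.5% | 107.7% |
| 14 | 4 | 12.22 | 152.7% | 101.8% |
| 14 | 8 | 12.11 | 151.4% | 100.9% |
| 14 | 52 | 12.02 | 150.2% | 100.1% |
| 16 | 8 | 10.75 | 134.4% | 89.6% |
| 21 | 8 | 8.40 | 105.0% | 70.0% |

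The 16-day and 21-day rows are illustrations. For the last row: 8 × 24 = 192 µg/kg over (7 × 21 + 13)/7 = 160/7 weeks.

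**Interval at which C1 reads 100% as written.** I(n−1) + 13 = 21n; at n = 8, I = (168 − 13)/7 = 22.1 days, against a planned 14.

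**Overall mean.** Assume 25 participants per cohort, each with eight on-schedule doses. Cohort A is 100.6% (X = 20). As written: (100.6 + 151.4)/2 = 126.0%. Divisor corrected: (100.6 + 100.9)/2 = 100.7% from unrounded values.

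**The residual above 100%.** The last column exceeds 100% on schedule because the SAR444245 duration is last dose + X − first dose. It lacks the extra day in SAP 3.6.1.1 ("first day of exposure +1)/30.4375") and is one day shorter than the pembrolizumab formula in 3.6.1.3, which adds 21. This alone gives Cohort A 105.0% at one dose and 100.1% at 35, and C1 107.7% at one dose and 100.1% at 52. With X = 14 and a 2-week divisor, on-schedule C1 RDI is exactly 100% at every n.

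**The case against.** The best defence is that the SAP's own definitions point to 2 weeks. The PDI wording refers to the theoretical cycle, and 3.6.1.1 places C1's next theoretical dose 14 days after the last one. A careful programmer could follow the definition and ignore the parenthesis. That is true, and the 1.5 factor arises only if the stated value is programmed. But a SAP should not leave the programmer to choose between a definition and the number it is said to equal.

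Second, the error would probably show itself: a cohort printing 150% to 162% on schedule invites a query. That holds for a well-dosed cohort. It fails where it matters most, because a participant at 70% prints an unremarkable 105%. The ADI, cumulative-dose, delay, omission and reduction summaries would still show the under-delivery, so RDI is not the only evidence.

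Third, the further consequences are conditional. Protocol 9.4.1 plans overall safety summaries only where applicable, so a pooled RDI row is not certain. The SAP defines no RDI cut-points, so misclassification cannot be demonstrated from the documents. Both limits stand.

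**Conclusion.** The concern holds. Taken at its stated value, the divisor inflates every Cohort C1 RDI by exactly 1.5; Cohort A is unaffected. The factor needs no assumption about doses or delays. The individual percentages assume full 24 µg/kg doses at the intervals shown, and the overall figure of 126.0% also assumes equal cohorts of 25 with eight on-schedule doses each.

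The reach is limited. SAP 3.6 makes the safety analyses descriptive, without testing. ADI, cumulative dose and the delay, omission and reduction tables do not use the divisor, and no efficacy endpoint, confidence interval, sample size or DLT rule depends on it. It should be corrected before the exposure tables are programmed, but it does not threaten the trial's conclusions.

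**What to change.** In SAP 3.6.1.2, give the PDI divisor as 3 weeks for Cohort A and 2 weeks for Cohort C1.

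Three small reconciliations can go into the same revision:

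- **Duration.** Set X to 21 for Cohort A and 14 for Cohort C1, or add one day to the formula, so that it agrees with 3.6.1.1 and 3.6.1.3.
- **Delay sub-categories (3.6.1.1).** A C1 delay counts from 3 days, as in Substudy 03 section 6.5.2, but the sub-rows begin at 4, so a 3-day C1 delay enters the total and no sub-row. Start the C1 sub-rows at 3 days.
- **Participant total (SAP section 4).** It gives about 75, but two cohorts of 25 make 50, and Table 3 in SAP 1.2.1 refers to two cohorts. Reconcile the total or name the third cohort if one is intended. No analysis uses the figure.

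The cost is a few words in the SAP and trivial programming, with no effect on trial conduct or on any dosing rule.
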